11.1 Pregnancy

It is not known whether bomedemstat can affect reproductive capacity, and the direct effects of bomedemstat and the indirect effects of prior bomedemstat exposure on fetal development are also unknown. Every effort should be made to prevent pregnancy throughout the entire duration of participation in this study. All patients of reproductive potential involved in the study are required to use effective methods of contraception during the study and for 30 days after the last bomedemstat dose.

Pregnancy testing requirements for study inclusion are described in Section 9.2. Additional serum or urine pregnancy tests may be performed, as determined necessary by the investigator or required by local regulation, to establish the absence of pregnancy at any time during the participant's participation in the study.

Although pregnancy and infant exposure during breastfeeding are not considered AEs, any pregnancy or infant exposure during breastfeeding (spontaneously reported to the investigator or their designee) that occurs in a participant during the study are reportable to the Sponsor.

All reported pregnancies must be followed to the completion/termination of the pregnancy.

Any pregnancy complication will be reported as an AE or SAE.

The medical reason (example: maternal health or fetal disease) for an elective termination of a pregnancy will be reported as an AE or SAE. Prenatal testing showing fetus will be born with severe abnormalities/congenital anomalies that leads to an elective termination of a pregnancy will be reported as an SAE for the fetus.

Pregnancy outcomes of ectopic pregnancy, spontaneous abortion, missed abortion, benign hydatidiform mole, blighted ovum, fetal death, intrauterine death, miscarriage, and stillbirth must be reported as serious events (Important Medical Events). If the pregnancy continues to term, the outcome (health of infant) must also be reported.

11.2 Adverse Events

The Investigator is responsible for monitoring the safety of patients who have enrolled in the study and for accurately documenting and reporting information as described in this section. Patients will be instructed to report to the Investigator any AE that they experience. Investigators will ask about the occurrence of AEs at each visit. Investigators are required to document all AEs occurring during the clinical study, commencing from the time of consent through 30 days post last bomedemstat dose (through the EoS/ED visit). AE recording will continue for patients who

discontinue study treatment early but remain in follow-up, until their EoT, Pre-EoS, and EoS Visits have been completed.

AEs will be recorded on designated eCRF pages. Each AE is to be characterized (*i.e.*, verbatim term) and information provided regarding its seriousness, start and stop dates, severity, outcome, and causal relationship with the study drug.

An AE is any undesirable physical, psychological or behavioral effect experienced by a patient during participation in an investigational study, in conjunction with the use of the drug or biologic, whether or not product related. This includes any untoward signs or symptoms experienced by the patient from the time of first dose with bomedemstat until completion of the study.

AEs may include, but are not limited to:

- Subjective or objective symptoms spontaneously offered by the patient and/or observed by the Investigator or medical staff
- Findings at PEs
- Laboratory abnormalities of clinical significance
- [REDACTED]
[REDACTED] No specific information is available on the treatment of overdose of bomedemstat. In the event of overdose, the participant should be observed closely for signs of toxicity. Appropriate supportive treatment should be provided if clinically indicated.
- Potential DILI events defined as an elevated AST or ALT laboratory value that is greater than or equal to 3× the ULN and an elevated total bilirubin laboratory value that is greater than or equal to 2× the ULN and, at the same time, an ALP laboratory value that is less than 2× the ULN, as determined by way of protocol-specified laboratory testing or unscheduled laboratory testing.

It is important Investigators record accurate AE terms in the eCRFs. Wherever possible, a specific disease or syndrome rather than individual associated signs, symptoms or laboratory parameter will be identified by the Investigator and recorded in the eCRF. However, if an observed or reported sign, symptom or laboratory parameter is not considered a component of a specific disease or syndrome by the Investigator, or is atypical, it should be recorded as a separate AE in the eCRF.

Disease signs, symptoms, and/or laboratory abnormalities already existing prior to the use of the IP are not considered AEs after treatment unless they reoccur after the patient has recovered from the preexisting condition or in the opinion of the Investigator they represent a clinically significant exacerbation in severity or frequency.

Clinical significance is defined as any variation in signs, symptoms, or testing that has medical relevance and may result in an alteration in medical care. The Investigator will continue to monitor the patient until the assessment returns to baseline or until the Investigator determines that follow-up is no longer medically necessary.

11.2.1 Adverse Event Severity

AE severity will be evaluated using the NCI CTCAE version 5, published 27-NOV-2017. For AEs not included in the NCI CTCAE, the Investigator will be required to assess the severity of the adverse drug/biologic experience using the following categories and associated guidelines:

Grade	Guideline
1	Mild; asymptomatic or mild symptoms; clinical or diagnostic observations only; intervention not indicated
2	Moderate; minimal, local or noninvasive intervention indicated; limiting age-appropriate instrumental ADL*
3	Severe or medically significant but not immediately life-threatening; hospitalization or prolongation of hospitalization indicated; disabling; limiting self-care ADL**
4	Life-threatening consequences: urgent intervention indicated
5	Death related to AE

Note 1: A semi-colon indicates 'or' within the description of the grade.

Note 2: Activities of Daily Living (ADL)

*Instrumental ADL refer to preparing meals, shopping for groceries or clothes, using the telephone, managing money, etc.

**Self-care ADL refer to bathing, dressing and undressing, feeding self, using the toilet, taking medications, and not bedridden.

11.2.2 Adverse Event Relatedness

The Investigator will make a judgment regarding whether or not, in his/her opinion, the AE was related to study drug. The Investigator will also evaluate any changes in laboratory values, make a determination as to whether the change is clinically significant, and whether or not the change(s) were related to study drug. However, even if the Investigator feels there is no relationship to the study drug, the AE or clinically significant laboratory abnormality MUST be recorded in the eCRF. Below are guidelines for relationship assessment:

- Unrelated: There was no relationship of the AE to the use of the drug or biologic. This may include, but is not limited to, the adverse experience being an expected outcome of a previously existing or concurrent disease, concomitant medication or procedure the subject experienced during their treatment period.
- Remote/Unlikely: AEs which are judged probably not related to the drug or biologic.
- Possible: There was no clear relationship of the AE to the use of the drug or biologic; however, one cannot definitively conclude that there was no relationship.
- Probable: While a clear relationship to the drug or biologic cannot be established, the event is associated with an expected AE (*per* the current Investigator Brochure or SAB findings) or there is no other medical condition or intervention which would explain the occurrence of such an experience.

- **Definite:** The relationship of the use of the drug or biologic to the experience is considered definitively established.

If a causal relationship is considered probable, possible, or definite by the Investigator or Sponsor (dependent on the regional reporting requirements), the AE is considered to be “related” for purposes of regulatory reporting. If a causal relationship is considered remote/unlikely or unrelated, the AE is considered “unrelated” for purposes of regulatory reporting.

11.2.3 Serious Adverse Events

SAEs will be reportable from the time of consent through the EoS Visit (scheduled for approximately 30 days post last bomedemstat dose) **or** until the Investigator and Sponsor determine that follow-up is no longer necessary. SAEs suspected to be drug related will be reported even if they occur when the patient is no longer on the study.

An SAE is any AE that results in any of the following outcomes:

- **Death**
- **Life-threatening experience.** Any AE that places the patient, in the view of the reporter, at immediate risk of death from the AE as it occurred, *i.e.*, does not include an AE that had it occurred in a more severe form, might have caused death.
- **Required or prolonged inpatient hospitalization.** The AE resulted in an initial inpatient hospitalization or prolonged an existing hospitalization of the patient. If a patient is hospitalized as part of the clinical use of the product, a period of normal hospitalization will be outlined in the protocol or by the judgment of the Investigator. Hospitalizations longer than this period will be prolonged hospitalizations.
- **Persistent or significant disability/incapacity.** An AE that resulted in a substantial disruption of a person’s ability to conduct normal life functions.
- **Congenital Anomaly.** The exposure of the patient to the drug or biologic during pregnancy that is judged to have resulted in the congenital anomaly/birth defect.
- **Important medical events.** AEs that may not result in death, be life-threatening, or require hospitalization may be considered an SAE when, based upon appropriate medical judgment, may jeopardize the patient or subject and may require medical or surgical intervention to prevent one of the outcomes listed above. Important medical events or interventions may be considered an SAE based upon medical judgment of the Investigator.

A hospitalization planned prior to time of consent is not considered an SAE. Surgeries or interventions requiring hospitalization under consideration but not performed prior to consent will not be considered serious if performed after consent **if** the condition has not changed in severity from its baseline level. If, however, the pre-planned hospitalization occurs after consent **and** an event occurs which prolongs hospitalization or meets any other SAE criteria, then the event will be considered an SAE.

11.2.4 Reporting Serious Adverse Events

SAEs will be reported promptly, using the SAE Report Form, once the Investigator determines that the event meets the protocol definition of an SAE. The Investigator or designee will report the SAE **within 24 hours of becoming aware of these events regardless of relationship of the SAE to the use of study drug**. A detailed SAE reporting procedure and contact information will be included in the SAE Report Form Completion Guidelines. The Investigator will always provide an assessment of relatedness at the time of the initial report as described in Section 11.2.2. The SAE Report will always be completed as thoroughly as possible with all available details of the event within the designated time frames. Copies of relevant patient records, autopsy reports, and other documents may be requested.

If the Investigator does not have all information regarding an SAE, they will not wait to receive additional information before reporting the SAE. The SAE Report will be updated when additional information is received **within 24 hours of receipt of such information**.

Important: For fatal and life-threatening events, the event should be reported in the EDC system immediately or within 24 hours of learning of the event. A death occurring during the study or information related to such occurrence that comes to the attention of the Investigator during the study must be reported immediately to the Sponsor. A detailed SAE reporting procedure and contact information will be included in the SAE Report Form Completion Guidelines and will be provided to the site before any patients are consented.

Additionally, the Institutional Review Board (IRB) and Independent Ethics Committee (IEC), as applicable, must be notified in writing of any SAEs that require expedited reporting to regulatory authorities. Depending upon regional requirements, it is the responsibility of the Investigator to notify the IRB/IEC. All SAEs meeting expedited reporting requirements will be reported to appropriate regulatory agencies by Sponsor or their designee as soon as possible and within the timeframes specified in the various regions in which the study is to be conducted.

11.2.5 For Participants Who Consent to An Extension Study

All AEs, SAEs, and other reportable safety events must be reported by the investigator in this protocol up to the time of consenting into a bomedemstat extension trial. Laboratory values that meet criteria for reporting as AEs performed during this study will be collected in this study.

Note: Once consented to an extension study, AEs/SAEs and other reportable safety events meeting the reporting criteria of the extension study, including those considered related to study intervention, will be collected in the extension study.

12 STATISTICAL METHODS

12.1 General Considerations

Detailed methodology for summary and statistical analyses of the data collected in this trial will be documented in a separate Statistical Analysis Plan (SAP). Additionally, a Pharmacokinetic Analysis Plan (PKAP) will be prepared. Baseline will be defined as the last non-missing observation closest to first dose and will be calculated in associated analysis. Descriptive statistics (arithmetic mean, standard deviation [SD], sample size, median, minimum, maximum, and number) will be calculated for continuous data, with frequency and percentages for categorical.

12.2 Power

This is a single-arm trial with a primary endpoint that is response rate as defined: incidence of patients who achieve a sustained reduction of Hct to <45% for 12 weeks without concomitant phlebotomy by Week 36.

In this study, approximately 20 participants will be enrolled and treated. With 15 observed responders, the estimated clinically meaningful response rate based on response rates for existing agents and its 95% CI are 75% (50.6%, 90.4%). All endpoints will be descriptive, and no formal hypothesis testing will be conducted. [Table 3](#) shows the two-sided 95% CIs for the response rates with 20 participants for different observed response rates based on the method of Clopper and Pearson. ([Clopper and Pearson, 1934](#)). Since this study does not have formal hypotheses to be tested, no power calculations have been conducted.

Table 3: Confidence Intervals for Different Observed Response Rates

Total Sample Size	Observed # of Responders	Observed Response Rate	95% CI (%)
20	13	65	(40.9, 83.7)
	14	70	(45.7, 87.2)
	15	75	(50.6, 90.4)
	16	80	(55.7, 93.4)
	17	85	(61.1, 96.0)
CI, confidence interval.			

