12.5 Primary Analysis

Incidence of patients who achieve a sustained reduction of Hct <45% for 12 weeks without concomitant phlebotomy by Week 36 will be summarized with point estimate and its 95% CI using exact binomial method proposed by Clopper and Pearson ([Clopper and Pearson, 1934](#)). Patients not achieving a response by Week 36 or dropping from the trial but have at least one post-baseline observation will be included in the analysis as a nonresponder.

[figure not shown]
AE verbatim terms will be coded using the Medical Dictionary for Regulatory Activities (MedDRA) and summarized by treatment emergent adverse event (TEAE), Serious TEAE, related TEAE, serious related TEAE, discontinued due to TEAE, TEAE by maximum toxicity grade. Patients will be counted once per unique preferred term and body system. TEAE is defined as any event that occurs on or after the first dose of study drug administration or any preexisting event which worsened in severity after dosing. Frequency and proportion of events will be summarized.

Changes in PEs, vital signs, and laboratory values will be analyzed over time where applicable. Shift tables to worst post-baseline may be produced for specific parameters as detailed in the SAP.

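### The intervals in Section 12.2 and Table 3 are labelled Clopper-Pearson but are Wilson intervals with continuity correction, so they do not match the method fixed for the primary analysis

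*Combined protocol and SAP*

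**What the plan says.** Section 12.2 (Power) says that "approximately 20 participants will be enrolled and treated". It takes 15 responders as its worked case and gives the interval as "existing agents and its 95% CI are 75% (50.6%, 90.4", that is, 50.6% to 90.4%. It then introduces Table 3, which "shows the two-sided 95% CIs for the response rates with 20 participants for different observed response rates", and names the method: "based on the method of Clopper and Pearson". Table 3 covers 13 to 17 responders out of 20. The section also states that endpoints are descriptive, that no hypothesis will be tested and that "no power calculations have been conducted".

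Section 12.5 (Primary Analysis) names the same method for the haematocrit response rate: a point estimate with its "95% CI using exact binomial method proposed by Clopper and Pearson".

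**The concern.** The Clopper-Pearson interval is fully determined by the responder count, the sample size and the confidence level, and Section 12.2 prints all three. The limits in Table 3 should therefore reproduce exactly, and they do not.

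Three things follow.

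- With no power calculation, these intervals are the only quantitative statement of what 20 patients can show.
- Section 12.5 commits the final analysis to the exact method. If 15 of 20 analysed patients respond, which is the protocol's own reference case, the report will show a different interval from the protocol. A reader could not tell which was wrong, or whether the method had been changed after the data were seen in an open-label trial.
- The Clopper-Pearson label promises at most 2.5% in each tail. The printed upper limits do not meet that.

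**Working it through.** **Inputs.** From Section 12.2: n = 20; x = 13, 14, 15, 16, 17 responders; two-sided 95% confidence, so 0.025 per tail; stated method Clopper-Pearson.

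**Step 1: the stated method.** The Clopper-Pearson limits are beta quantiles:

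- lower = 0.025 quantile of Beta(x, n − x + 1)
- upper = 0.975 quantile of Beta(x + 1, n − x)

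For x = 15, the lower limit is the 0.025 quantile of Beta(15, 6) = 50.90%, and the upper limit is the 0.975 quantile of Beta(16, 5) = 91.34%. At each computed limit, for all five counts, the binomial tail probability came back as 0.025.

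**Step 2: reproducing the printed figures.** The Wilson score interval with continuity correction, with p = x/n, q = 1 − p and z = 1.96, is:

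- lower = [2np + z² − 1 − z√(z² − 2 − 1/n + 4p(nq + 1))] / [2(n + z²)]
- upper = [2np + z² + 1 + z√(z² + 2 − 1/n + 4p(nq − 1))] / [2(n + z²)]

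For x = 15: p = 0.75, np = 15, nq = 5, z² = 3.8415, and the denominator is 2 × 23.8415 = 47.683.

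- lower = [30 + 3.8415 − 1 − 1.96 × √(3.8415 − 2 − 0.05 + 18)] / 47.683 = (32.8415 − 8.719) / 47.683 = 50.59%
- upper = [30 + 3.8415 + 1 + 1.96 × √(3.8415 + 2 − 0.05 + 12)] / 47.683 = (34.8415 + 8.267) / 47.683 = 90.41%

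These round to the printed 50.6 and 90.4.

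**Step 3: all five rows (%).**

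| x/20 | Table 3 | Clopper-Pearson | Wilson with continuity correction | Table 3 minus Clopper-Pearson (lower, upper) |
|---|---|---|---|---|
| 13 | 40.9, 83.7 | 40.78, 84.61 | 40.95, 83.69 | +0.12, −0.91 |
| 14 | 45.7, 87.2 | 45.72, 88.11 | 45.67, 87.16 | −0.02, −0.91 |
| 15 | 50.6, 90.4 | 50.90, 91.34 | 50.59, 90.41 | −0.30, −0.94 |
| 16 | 55.7, 93.4 | 56.34, 94.27 | 55.73, 93.39 | −0.64, −0.87 |
| 17 | 61.1, 96.0 | 62.11, 96.79 | 61.14, 96.04 | −1.01, −0.79 |

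The Wilson lower limit for 13/20 is 40.949 to three decimals, which rounds to the printed 40.9. All ten printed limits therefore match that method. Only one, the lower limit for 14/20, also matches Clopper-Pearson.

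**Step 4: tail probability at the printed upper limits.** If the true rate equalled the printed upper limit, the exact probability of x or fewer responders would be 0.033, 0.035, 0.037, 0.039 and 0.044 for x = 13 to 17. Clopper-Pearson sets each of these at 0.025.

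**Step 5: other explanations.**

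- Plain Wilson, Agresti-Coull, Jeffreys, mid-P, Wald and Wald with continuity correction at n = 20 do not reproduce the table.
- A different denominator does not help: Clopper-Pearson gives (54.43, 93.95) for 15/19 and (47.82, 88.72) for 15/21.
- Nor does a different level: 15/20 at alpha 0.04, 0.06 and 0.10 gives (49.84, 91.82), (51.79, 90.92) and (54.44, 89.59).
- The 15/20 interval appears identically in the sentence and in the table, so it is not a damaged cell.
- The protocol's other binomial intervals, in Section 3.5.1, do reproduce as Clopper-Pearson: 12/45 (14.6, 41.9), 11/39 (15.0, 44.9) and 1/6 (0.4, 64.1). Among the intervals checked, the fault is confined to Section 12.2 and Table 3.

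**The case against.** The arithmetic is not in dispute; the weight is. The trial is descriptive, and no threshold, go/no-go rule or sample-size derivation uses these limits. The interim analysis in Section 12.8 is descriptive too. No limit moves by more than about one percentage point, on intervals roughly 35 to 44 points wide. Widths barely change: 39.8 printed against 40.4 exact for 15/20, and at 17/20 the printed interval is slightly wider (34.9 against 34.7). The lower limit for 15/20 stays above 50% either way. The sample size, responder counts and observed rates are correct. The protocol does not say that 20 was chosen for precision. Section 12.5 is unambiguous, so a report that follows it will be right whatever Table 3 shows. Finally, the enrolment target is approximate, and the primary population in Section 12.4 requires a post-baseline result. If the analysed number is not 20, the reported interval will differ from Table 3 under any method.

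All of this stands as a limit on consequence. None of it makes the printed figures what they are said to be, and nothing elsewhere in the protocol corrects them.

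**Conclusion.** The concern holds. No row of Table 3 is a Clopper-Pearson interval: nine of ten limits are wrong at the printed precision, and the interval in the text is wrong at both ends. The upper limits are too low by 0.8 to 0.9 points. The lower limits are off by between +0.1 and −1.0 points, with 14/20 agreeing to one decimal. The reference case should read 75% (50.9%, 91.3%).

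The arithmetic needs no assumption beyond the inputs printed in Section 12.2. The predicted mismatch between protocol and report assumes that exactly 20 patients are analysed. This is an error of correctness and traceability in the study's only precision figures; it does not threaten the design or the planned analysis.

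**What to change.** Keep Clopper-Pearson as the method and correct the numbers. Table 3 becomes:

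| Responders out of 20 | Observed rate (%) | 95% CI (%) |
|---|---|---|
| 13 | 65 | (40.8, 84.6) |
| 14 | 70 | (45.7, 88.1) |
| 15 | 75 | (50.9, 91.3) |
| 16 | 80 | (56.3, 94.3) |
| 17 | 85 | (62.1, 96.8) |

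In the text of Section 12.2, change the 15-responder interval to 75% (50.9%, 91.3%).

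Relabelling the table as Wilson with continuity correction would be the wrong repair, because it would leave Section 12.2 at odds with Section 12.5. Section 12.5 needs no change. If the program that produced Table 3 is to be reused for the interim or final analysis, confirm that it calls the exact method.

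The cost is one table and one sentence, with no operational change.
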